7.3 LOST TO FOLLOW-UP

A participant will be considered lost to follow-up if he or she fails to return for the final, 12-month follow-up assessment. If a participant misses intervention calls or follow-up assessments prior to the 12-month time point and cannot be contacted during the time frame, the study team will still attempt to contact the participant for remaining calls / assessments. The study team must attempt to contact a participant at least 3 times, on different days of the week, different times of day, and across at least 2 weeks, before they are considered to have missed a visit / assessment or be lost to follow-up. These contact attempts will be documented in the study database.

8 STUDY ASSESSMENTS AND PROCEDURES

8.1 ENDPOINT AND OTHER NON-SAFETY ASSESSMENTS

Measures will be collected at baseline, 6-months and 12-months by a trained research assistant blinded to randomization assignment. Other than the accelerometer, measures will be administered via phone. Participants will be paid \$25 for completing each phone-based measure and \$15 for returning the accelerometer device at each time point.

Primary Efficacy Outcome: Objectively Assessed Physical Activity.

We selected this as the primary study outcome because PA is the target of the intervention, and objective assessment has advantages over self-report in terms of accuracy⁸⁶. Our specific primary outcome of interest is minutes of moderate to vigorous intensity PA (MVPA) per week, since this corresponds to DHHS recommendations and is a known predictor of outcomes in patients with OA⁷⁸. We will also examine step counts, minutes of sedentary activity and other complementary metrics, as these are also important for providing a broad picture of PA among participants^{80,87}. Each participant will be asked to wear the Actigraph GT3X+ (Pensacola, FL), which allows for the collection and manipulation of raw actigraphy data to facilitate accurate assessment of PA⁸⁸. Participants will be asked to wear the monitors during all waking hours for 7 days. Following previously established thresholds, outcomes will only be computed for participants who wear the accelerometer for 4+ days with 10+ hours of daytime wear. Monitors will be worn on the waist, using either an elastic belt or clip, over the right hip. We may ask a subset of participants to wear a wrist-worn monitor in addition to the waist-worn monitor, in order to assess acceptability and compare values obtained from monitors worn at the two different sites. Accelerometers will be mailed with instructions and a pre-stamped / addressed return envelope. Several days after the accelerometer has been mailed, a study team member will call the participant to review instructions. A phone number will be provided for problems or questions. A second call will be made toward the end of the 7 days to ask about wear and to remind participants to return the monitor. If participants have not worn the monitor enough, they will be asked to wear the monitor a few extra days. Drs. [name], [name] and [name] have been involved with projects that have successfully mailed accelerometers to and / or from study participants with OA. There have been high rates of adherence (4+ days with 10+ hours of wear); 93% in one study of adults and partners with OA and 89% in another of 140 patients with OA, with

minimal loss of monitors (< 2%). In Aim 2 of this project, valid accelerometer data were available for 57 participants at baseline (95%) and 52 participants at follow-up (86%). Upon return, accelerometer data will be downloaded, compiled into 60s epochs, processed to identify wear, non-wear, and sleep periods using current algorithms^{89,90}, and summarized using cut-points developed by Troiano⁸⁹ and Mathews⁹¹. These cut-points will allow us to calculate minutes of MVPA, as well as sedentary time and step counts.

Secondary Efficacy Outcomes:

Self-Reported Physical Function. Physical function is a key outcome in OA and can be improved with regular PA^{14,15}. We will assess physical function with the widely used Western Ontario and McMaster Universities Osteoarthritis Index (WOMAC) subscale^{92,93}; it includes 17 items, rated on a Likert scale of 0 (no difficulty) to 4 (extreme difficulty), that assess difficulty with performing a range of daily activities commonly affected by lower extremity OA. The reliability and validity of the WOMAC total score and subscales have been confirmed⁹³. In patients with hip or knee OA, Bellamy et al. reported internal consistency coefficients (Cronbach's alpha) between 0.86 and 0.95 on WOMAC subscales.

Pain (WOMAC). We will assess self-reported pain using the WOMAC subscale^{14,15}; it includes 5 items, rated on a Likert scale of 0 (no pain) to 4 (extreme pain), that assess pain during a range of daily activities.

Exploratory Outcomes:

Stanford Numeric Rating Scale (NRS) for Fatigue: We will assess self-reported fatigue using the Stanford NRS Scale for Fatigue; it includes 1 item, rated on a Likert scale of 0 (no fatigue) to 10 (severe fatigue), that assesses fatigue in the past 2 weeks.

Self-reported Physical Activity: Modified version of the CHAMPS (Community Health Activities Model Program for Seniors) Physical Activity Measure⁹⁴. This measure complements the accelerometer-based data by providing additional information on the contexts and types of activities in which participants are engaging. This modified version of the CHAMPS includes items tailored for this participant group. For each item, participants first indicate whether they have done the activity for 10 or more minutes during the past week. If they respond "yes," they will be asked the number of days and minutes per week. This questionnaire will be supplemented with individual items to assess sitting behavior and sleep.

Patient Global Impression of Change. We will use this scale to evaluate participants' perspectives on overall changes in their joint pain during the study period. This measure asks participants to describe their change in pain on a 7-point rating scale with the following options: "very much improved," "much improved," "minimally improved," "no change," "minimally worse," "much worse," and "very much worse." This scale has been widely used in clinical trials of chronic pain and is recommended by IMMPACT.

Pain Medication Use. Pain medications are a common treatment for patients with OA, and some patients seek to reduce their use; therefore we have included this as an exploratory outcome. We will assess pain medication use using methods we have used successfully in previous studies. We will ask participants to bring to the telephone all medications (prescription and non-prescription) they are currently taking for their arthritis symptoms. For each medication, the study team will record the medication name, medication class, frequency of taking the medication.

PROMIS Sleep Disturbance – Short Form 4a. The PROMIS adult sleep related impairment item bank focuses on self-reported perceptions of sleep quality, sleep depth, and restoration associated with sleep. It assesses sleep-related impairment over the past seven days. This scale includes 4 items, each measured on a 5-point Likert scale.

Potential Mediators and Moderators of Intervention Effects:

We are interested in understanding the roles of various “active ingredients” of the OA-PCP (mediators), as well as potential patient characteristics that are associated with differential effectiveness (moderators). With respect to mediators, we will assess number of OA-PCP calls completed, participants’ ratings of satisfaction and helpfulness of the calls (single item numeric rating scales of 0-10), indicators of whether participants engaged with new group-based or self-directed PA resources during the study, and participants’ ratings of satisfaction and helpfulness of any new PA resources they have tried. These variables will be assessed at both 6 and 12 months. With respect to moderators, we are particularly interested in variables of age, gender and level of baseline PA, but we will also conduct additional exploratory analyses of heterogeneity of treatment effects, as described below.

Participant Characteristics:

We will collect the following information to characterize the study sample: age, race / ethnicity, gender, education, works status, marital status, body mass index, comorbid illnesses⁹⁵, joints with arthritis symptoms and duration of knee / hip OA symptoms, as well as:

Covid-19 Impact Scale. The scale was designed to rate the impact of the COVID-19 pandemic, deferring to other well validated scales to assess general stress or symptoms developed in response to the pandemic. This scale includes 1 item with the following options: “Reduced my ability to get be physically active a lot”, “Reduced my ability to get be physically active a little”, “not affected my ability to be physically active” or improved my ability to be physically active”.

Valuing Questionnaire. The Valuing Questionnaire assess the extent of personal values enactment during the past-week. This questionnaire lists 10 life domains (e.g., family relations, physical well-being). Participants rate the importance of each domain and how consistently they have lived according to their values in that domain during the past week (on a scale of 0–10).

Feasibility and Acceptability:

The following metrics will inform *feasibility*:

- Proportion of screened patients who meet the PA eligibility criterion (<150 min per week)
- Proportion of screened patients who are eligible overall
- Proportion of patients who consent to participate, along with refusal reasons for those who do not
- Proportion of participants who complete each phase of the intervention and follow-up assessments

We have developed open-ended questions to assess *acceptability* of the intervention. Topics include acceptability of each intervention component, usefulness of options provided for PA programs / resources, and suggestions for increasing the patient-centeredness of the intervention.

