6.3 MEASURES TO MINIMIZE BIAS: RANDOMIZATION AND BLINDING

The randomization scheme will be generated by the study statistician and stored within the study database. The database will be configured so that blinded study personnel (e.g., those conducting follow-up assessments) will not have access to randomization information. The participants will not be notified of randomization assignment until all baseline assessments are complete. In addition, an individual participant's randomization assignment will not be known to any study personnel until baseline assessments are complete. Randomization will be stratified according by clinic site.

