Exploration of Mediators. We are interested in understanding the degree to which various facets of the OA-PCP contribute to improvements in PA and other outcomes. Because the mediating variables of interest (described above) pertain only to the OA-PCP group, our strategy will differ from a traditional mediation analysis approach in the context of a clinical trial. Specifically, we will use linear regression models to assess associations between potential mediating variables and outcomes among individuals in the OA-PCP group. Each potential mediator will be assessed individually, then we will fit a multivariable model including all variables with bivariate associations of $p \leq 0.1$. Analyses will be performed for both 6 and 12 month outcomes.

Exploration of Moderators. We will explore potential differential treatment effects based on participant characteristics, particularly gender, age and baseline PAVS score. The latter is of interest to help inform the inclusion criterion for a larger trial; if individuals with higher baseline PA (though not meeting DHHS recommendations) make little additional improvement in PA, we may focus on individuals with lower PA levels at screening. For assessment of differential treatment effects, we will conduct stratified analyses based on participant characteristics (e.g., men / women, age categories by decade, quartiles of baseline PAVS scores). We propose this strategy because the study is not powered to detect interactions between treatment group and participant characteristics. We will also use multivariable logistic regression^{104,105} and recursive partitioning (RP)^{106,107} to explore multidimensional subgroups that exhibit heterogeneous treatment effects; these analyses will focus on our a priori characteristics of interest but also explore additional variables.

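### The blinded assistant's 6- and 12-month phone interviews include items that can reveal the arm, and the plan has no safeguard against this

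*Combined protocol and SAP*

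**What the plan says.** Section 8.1 opens with a rule that has no exception: "Measures will be collected at baseline, 6-months and 12-months by a trained research assistant blinded to randomization assignment". On mode it adds: "Other than the accelerometer, measures will be administered via phone".

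Under its mediator paragraph, the same section says: "With respect to mediators, we will assess number of OA-PCP calls completed". It goes on to list participants' "ratings of satisfaction and helpfulness of the calls", whether they took up new PA resources, and how they rated those resources. On timing it says: "These variables will be assessed at both 6 and 12 months". Under feasibility and acceptability, it adds open-ended questions about each component of the intervention and the usefulness of the PA options offered.

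Section 9.4 (Exploration of Mediators) explains that the mediator analysis is confined to one arm because the variables "pertain only to the OA-PCP group".

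Section 6.3 gives the safeguard. The database is to be set up so that "blinded study personnel (e.g., those conducting follow-up assessments) will not have access to randomization information".

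The schedule of activities (section 1.3) marks the mediator/moderator row and the acceptability row at Visit 11 (12 months) only, with no mark at Visit 8 (6 months).

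**The concern.** Participants are told their assignment, and the secondary outcomes (WOMAC pain and function, hypothesis H2) are spoken answers given to an interviewer. Blinding the interviewer is meant to stop knowledge of the arm from affecting how questions are put, probed or recorded. If the same interview contains questions that apply to one arm only, then asking them, skipping them or hearing the answers tells the interviewer which arm the participant is in. A lock on the database does not prevent that.

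At stake is the claim of blinded assessment for WOMAC and for the exploratory phone measures: fatigue, sleep, self-reported activity, global change and pain medication. Baseline is not at issue, because section 6.3 keeps assignments unknown to all staff until baseline assessments are complete. The primary outcome, accelerometer minutes of moderate to vigorous activity, depends little on who conducts the interview.

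**Working it through.** No figure in the plan is in dispute, so the check is a comparison of sections.

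**Step 1. Who asks.** Section 8.1 names one role for its measures at all time points, a blinded assistant working by phone. No section gives the mediator or acceptability items to anyone else. Unblinded team members do exist and already telephone participants: section 5.5 uses them for the assignment and tracker calls, and section 6.4 for chasing missed intervention calls.

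**Step 2. Which items can reveal the arm.**

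| Item | Must it come from the participant? | Can it reveal the arm? |
|---|---|---|
| Number of OA-PCP calls completed | No; section 6.4 tracks intervention contacts in the database | Not through the interview |
| Satisfaction with and helpfulness of calls | Yes | Yes if asked in one arm only; possibly through the answers if asked in both |
| Use and ratings of new PA resources | Yes | As above |
| Open-ended acceptability questions | Yes | Yes; they ask about components and PA options, and the answers are free text |

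Section 9.4 treats the mediator items as applying to OA-PCP only. On that reading, their presence or absence in the interview identifies the arm.

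**Step 3. What protects the blind.** Section 6.3 restricts database access. No section fixes the order of items within a call, asks participants not to disclose their arm, or says how unblinding is recorded.

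**Step 4. Which outcomes are exposed.** This depends on timing, on which the sections conflict.

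- *Section 8.1 followed (mediator items at 6 and 12 months).* The 6-month WOMAC is exposed if the items come before it in that call. The 12-month WOMAC is exposed if they come before it in that call, if the assistant who asked them at 6 months also makes the 12-month call, or if the information passes through records.
- *Section 1.3 followed (12 months only).* These items expose nothing at 6 months. The 12-month WOMAC is exposed only if they are asked before it in the same call.
- *Acceptability items.* Section 1.3 places them at 12 months, so the same question of order applies.

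The plan states neither the order of items nor whether one assistant makes both calls. Unblinding is therefore possible under both schedules, and under neither is it bound to precede an outcome.

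**The case against.** The strongest reply is that this is an unspecified detail rather than a breach of blinding.

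- **The items could be asked of everyone.** Section 6.1 gives controls the same number and duration of calls and emails, so 0-10 call ratings could be put to both arms. Any participant can say whether they tried a new PA resource. The sentence in section 9.4 explains a restricted analysis and does not say who is asked what. Also, where the schedule means one arm only (the activity tracker row) it says so, and the mediator and acceptability rows carry no such label. This stands as a possibility, and adopting it would reduce the problem. But the plan does not say it, section 9.4 points the other way, and free-text answers about components could still reveal the arm.
- **Call counts need no interview.** This stands. It removes one item and leaves the ratings.
- **The assessor may change.** Section 8.1 describes a role and section 6.3 refers to assessors in the plural. This stands against any claim that 6-month unblinding must carry over to 12 months. It does not address the order of items within one call.
- **Participants already know their arm.** WOMAC uses fixed response options, the participant's own knowledge reaches the answers whoever asks, and the attention control deals with general contact effects. All true, and it limits what assessor blinding can achieve. It is still a protection that the plan claims, and the interviewer's influence is a separate route.
- **Only secondary and exploratory outcomes are involved, in a trial that section 9.2 calls exploratory.** This stands and limits the priority of the point.

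**Conclusion.** The concern holds as a gap in protection. Followed as written, section 8.1 has a blinded assistant conduct an interview that can itself reveal the arm, and section 6.3 guards only the database. The mediator timing in sections 1.3 and 8.1 also conflicts and needs correcting in any case.

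A reader might infer more, and the documents do not support it:

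- *That the assessor is bound to learn the arm before the 12-month WOMAC, or that blinding ends for the whole OA-PCP arm at 6 months.* The schedule shows no mediator items at 6 months, no section says the same assistant calls twice, and the order of items is not given.
- *That the bias can be sized against the effect of 0.38 in section 9.2.* That figure is for minutes of moderate to vigorous activity, the outcome least affected here. The sample size was chosen on feasibility, with power described for it. Any assumed WOMAC shift would be invented.

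The size of any bias therefore cannot be estimated from the documents. The exposure is confined to phone-administered WOMAC and exploratory self-reports. The conclusion rests on two assumptions: that the section 8.1 rule on who collects measures covers the mediator and acceptability items, as its wording implies, and that no unseen procedure (for instance in the Manual of Procedures) already separates them. It is an inexpensive improvement worth making, and it does not threaten the primary analysis.

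**What to change.** 1. Reconcile section 1.3 with section 8.1 on whether the mediator items are collected at 12 months only or at both 6 and 12 months.
2. State in sections 6.3 and 8.1 that OA-PCP-specific mediator items and acceptability items are collected only after the outcome interview at that time point is closed. Use an existing unblinded team member who is not the coach, or a separate mailed or REDCap form. Take call counts from the study database.
3. Keep those responses hidden from blinded assessors, so that 6-month answers cannot inform the 12-month interviewer.
4. Record any unblinding of an assessor, with the time point and whether it came before or after the outcome measures.

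The cost is protocol wording and a short extra contact or form at one or two time points, depending on how item 1 is settled, with slightly more participant burden. Existing staff can do it. Sample size and power are unchanged.

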8.2 SAFETY ASSESSMENTS

The study PA coach will be trained to deliver the interventions in adherence to and within the scope of the intervention. If a study team member learns of any adverse events (AEs) that occur in the course of participants’ home exercise, this will be documented on the Adverse Events form, as described below.

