5.5 STRATEGIES FOR RECRUITMENT AND RETENTION

Potential participants will first be identified using the electronic medical record (EMR). Specifically, we will identify patients age 65 and older with diagnosis codes for knee or hip OA (M17.0, M17.10, M17.11, M17.12, M17.2, M17.30, M17.31, M17.32, M17.4, M17.5, M17.9, M16.0, M16.10, M16.11, M16.12, M16.2, M16.30, M16.31, M16.32, M16.4, M16.50, M16.51, M16.52, M16.6, M16.7, M16.9, M19.90, M19.91, M19.92, M19.93, M15.0 (primary, generalized OA)), a diagnosis code for at least one qualifying comorbid health condition under CCM guidelines listed above, and no diagnosis codes for exclusionary health conditions. We will include patients who have been seen within UNC by a primary care provider during the past 2 years, including Internal Medicine, Family Medicine and Geriatrics clinics. Primary care providers may, if they choose, review lists of patients eligible based on the EMR and approve a final list of patients to contact, but this is not a requirement. These patients will be mailed an introductory letter and then called by a study team to further assess eligibility. Patients who are eligible and interested in participating will complete a verbal consent process which will include verbal HIPAA authorization. Then participants will complete baseline assessments via telephone and be mailed an accelerometer for physical activity assessment. Participants will be paid \$25 for completing each phone-based assessment and \$15 for returning the accelerometer at each time point. Following return of the accelerometer at baseline, an unblinded study team member will call the participant to inform them of their randomization assignment. Participants assigned to the OA-PCP group will then be mailed an Activity Tracker and instructions and asked to begin wearing it as soon as they receive it. About a week after the Activity Tracker is mailed, an unblinded study team member will call the participant to answer any questions about device wear and setup. We will aim for the participant to wear the Activity Tracker for at least 1 week prior to the first OA-PCP call, so that PA goals can be based on current activity patterns. Participants will also be notified that the PA Coach will be able to view their Activity Tracker data using Fitabase®.

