2. *PA Goal-Setting:* The Coach will work with participants to establish and document PA goals, with an initial focus on the next 2 weeks (before check-in call; Figure 3). Participants will be asked to focus their PA goals on either step counts or activity minutes; monitoring for each of these will be facilitated by use of the Activity Trackers. Recent research has identified important metrics for reducing risks of functional limitation and disability among individuals with OA. In particular, thresholds of 60 weekly minutes of MVPA and 6,000 steps per day as important targets^{79,80}. Participants will be asked to select one of these benchmarks as a minimum goal to work toward during the one-year time period of the intervention. If participants meet one of these goals, they will be encouraged to work toward broader public health goals of 150 minutes of MVPA per week or 7,500-10,000 steps per day^{76,77}. Participants may also switch from step-focused goal to an activity minute-focused goal as the OA-PCP calls progress. As noted above, initial goals will be based on participants' current PA data (e.g., at least 1 week of Activity Tracker wear). The PA Coach will inform participants that s/he will be able to monitor their PA (using Fitabase®), with their permission, based on data from the Activity Tracker, and describe that this will enhance the "partnership" of this program, allowing the Coach to observe specific PA patterns and potential opportunities to enhance activity during the day. As part of the goal-setting process, the Coach will talk with participants about potential barriers and use a problem-solving approach to address each one.

3. *Discussion of Preferences for PA and Identifying Appropriate PA Resources:* The Coach will ask participants brief questions to understand types of PA they enjoy most and are likely to engage in. Based on this information, at the 2-week call, the Coach will recommend specific PA programs resources that can help them progress toward their PA. The coach will also review participants' progress toward PA goals and set new goals. If participants have encountered any barriers to PA since the first call, they will be addressed and other PA resources identified if needed.

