6.2 FIDELITY

PA Coach(es) will be trained by [name] and will conduct mock sessions of all OA-PCP calls prior to study initiation. We plan to audio record calls for approximately the first 10 participants and a random subset thereafter. [name] and another investigator with experience in delivering behavioral PA interventions ([name] or [name]) will review audio recordings and provide feedback to the PA Coach. A similar process will be used for the attention control calls, with a particular emphasis on ensuring that OA-PCP content is not included in these calls.

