8.3 ADVERSE EVENTS AND SERIOUS ADVERSE EVENTS

8.3.1 DEFINITION OF ADVERSE EVENTS

This protocol uses the definition of adverse event from DHHS Office for Human Research Protections (OHRP): Any untoward or unfavorable medical occurrence in a human subject, including any abnormal sign (for example, abnormal physical exam or laboratory finding), symptom, or disease, temporally associated with the subject’s participation in the research, whether or not considered related to the subject’s participation in the research (modified from the definition of adverse events in the 1996 International Conference on Harmonization E-6 Guidelines for Good Clinical Practice).

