8.3.4 TIME PERIOD AND FREQUENCY FOR EVENT ASSESSMENT AND FOLLOW-UP

The occurrence of an AE or serious adverse event (SAE) may come to the attention of study team members during study visits. All AEs, not otherwise precluded per the protocol, will be captured on the Adverse Event Form. Information to be collected includes event description, time of onset, PI or co-investigator's assessment of severity, relationship to study procedures (assessed only by those with the training and authority to make a diagnosis), and time of resolution/stabilization of the event. All AEs occurring while on study will be documented appropriately regardless of relationship. All AEs will be followed to adequate resolution.

Any medical or psychiatric condition that is present at the time that the participant is screened will be considered as baseline and not reported as an AE. However, if the study participant's condition deteriorates at any time during the study, it will be recorded as an AE.

Changes in the severity of an AE will be documented to allow an assessment of the duration of the event at each level of severity to be performed. Documentation of onset and duration of each episode will be maintained for AEs characterized as intermittent.

The Project Coordinator will record events with start dates occurring any time after informed consent is obtained until 7 (for non-serious AEs) or 30 days (for SAEs) after the last day of study participation. Participants are identified in the EMR as a study participant and for each AE/SAE occurrence, research team members will receive an alert through EMR. AEs or SAEs may also be reported to PA Coach during the course of intervention visits. Events will be followed for outcome information until resolution or stabilization.

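### Sections 8.2 and 8.3 disagree on which adverse events are recorded, and passive capture gives minor events more occasion to surface in the OA-PCP arm

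*Combined protocol and SAP*

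**What the plan says.** **Scope.** Section 8.2 opens its recording rule with "If a study team member learns of any adverse events (AEs) that occur in the course of" home exercise and sends such events to the adverse event form. Section 8.3.1 adopts a definition that takes in any untoward occurrence "temporally associated with the subject’s participation in the research, whether or not considered related to the subject’s participation in the research". Section 8.3.4 states: "All AEs occurring while on study will be documented appropriately regardless of relationship". It also counts deterioration of a condition present at screening.

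**How events are found.** Section 8.3.4 says events "may come to the attention of study team members during study visits", can be told to the PA coach during intervention contacts, and trigger an alert to the team through the electronic medical record (EMR). The Schedule of Activities (1.3) marks adverse event reporting from Visit 2 to Visit 11, with no split by arm. That includes the 6- and 12-month assessments, which 8.1 gives to a blinded research assistant.

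**What each arm's contacts cover.** Section 6.1 matches the number and duration of calls and emails. OA-PCP calls review progress, and at the 2-week call: "If participants have encountered any barriers to PA since the first call, they will be addressed". The 6-month OA-PCP call deals with setbacks. Control calls cover other OA topics, and 6.2 has recordings of them reviewed "with a particular emphasis on ensuring that OA-PCP content is not included in these calls". The OA-PCP arm alone has the set-up contact in 5.5: "About a week after the Activity Tracker is mailed, an unblinded study team member will call the participant". It may also contact the coach at any time about activity resources (6.1).

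**The concern.** Two things look wrong. First, staff who work from 8.2 and staff who work from 8.3.4 would record different sets of events. Second, when nobody is required to ask, an event is recorded only if the participant has a reason to bring it up. A call about activity, barriers and setbacks supplies that reason for the harms named in 2.2.1 (injury, muscle soreness, joint pain). A call kept clear of activity content supplies less of it.

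The counts have uses even though no test is planned. Sections 8.3.3.3 and 8.4.1 judge expectedness partly by frequency. Section 10.1.6 sends all events to the Safety Officer twice a year. Section 10.1.2 allows suspension for unacceptable risk. Section 9.2 presents the trial as preparation for a larger one, which will want a usable estimate of harm in people aged 65 and over. If events are tabulated by arm, a difference in harm cannot be separated from a difference in the chance of mentioning it.

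**Working it through.** **Step 1: scope.** Take a flare of joint pain at rest in a control participant. Sections 8.3.1 and 8.3.4 put it on the form; the sentence in 8.2 does not reach it. Section 8.2 contains no word such as only, and it points forward to 8.3. This is therefore an inconsistency to reconcile, not a protocol-wide limit.

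**Step 2: routes, compared by arm.**

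- Intervention calls (6.1): equal in number and length, different in content.
- Tracker set-up call (5.5) and open access to the coach about resources (6.1): OA-PCP only.
- 6- and 12-month assessment calls (8.1; Visits 8 and 11): same in both arms, blinded, marked for adverse event reporting, but with no adverse event item among the measures in 8.1.
- EMR alert (8.3.4): same in both arms, but it sees only what reaches that record. Whether it covers all the recruiting networks is not stated.

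The first two routes favour mention of exercise-type events in OA-PCP. The last two are neutral. So the likely direction, for minor events, is more recorded events in OA-PCP.

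**Step 3: size, by illustration.** The documents give no event rate, capture rate or adverse event analysis, so there is no stated figure to reproduce. The only input from the plan is 120 per group (9.2); every rate below is assumed.

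Let the true risk p be equal in both arms, with capture s1 in OA-PCP and s0 in control. Expected recorded events are 120 × p × s. The recorded risk ratio is s1/s0, because p cancels. With p = 0.20:

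- 80% v 80%: 120 × 0.20 × 0.80 = 19.2 in each arm; ratio 1.00.
- 80% v 60%: 19.2 v 120 × 0.20 × 0.60 = 14.4; ratio 0.80/0.60 = 1.33.
- 80% v 40%: 19.2 v 120 × 0.20 × 0.40 = 9.6; ratio 0.80/0.40 = 2.0.

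Now let the EMR alert catch a share e of events equally in both arms, whether or not they are mentioned on a call. Capture becomes e + (1 − e) × s. For the 80% v 40% case:

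- e = 0.25: 0.85/0.55 = 1.55
- e = 0.50: 0.90/0.70 = 1.29
- e = 0.75: 0.95/0.85 = 1.12
- e = 1: 1.00

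The bias depends on two quantities that the documents do not give: the gap in capture on calls, and the share of events reaching the EMR.

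**The case against.** The case on the other side is substantial, and several stronger readings fail against it.

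- A reader might infer that a planned harm comparison is biased. Section 9.4 plans none. Events are assessed one by one (8.3.3) and reported to the Safety Officer. What stands is that any summary by arm could be biased.
- A reader might infer that one arm is asked and the other is not. No passage shows either arm being asked. The difference is in occasion to volunteer.
- A reader might infer that the 6- and 12-month calls are unused for safety. The schedule marks them for it; what is missing is a question.
- A reader might take the ratio of 2.0 as an estimate. It is the result of assumed rates with no EMR capture, and shared capture reduces it.
- A reader might infer that marked worsening on the Patient Global Impression of Change, which measures "overall changes in their joint pain during the study period", must open an adverse event form because 8.3.4 counts deterioration. The documents do not make that link. Adding it to an exploratory outcome in a chronic painful condition is a debatable preference.

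Two further points also have force. Control topics include pain medication, mechanical treatments, and sleep and fatigue, which can also draw out symptoms. So the direction is plausible for exercise-type events but not shown for adverse events in general. The adverse event form, call scripts and Manual of Procedures are not among the documents, so a scripted question may exist there. Neither point removes the mismatch between 8.2 and 8.3, or the absence from the plan itself of a common method of asking.

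**Conclusion.** The point holds in limited form. Section 8.2 and sections 8.3.1 and 8.3.4 differ in scope and must be reconciled. Capture from participants is passive as written. Equal call dose does not equalise the prompt to mention soreness, joint pain or minor injury, so any by-arm summary of non-serious events could be biased, most likely towards more recorded events in OA-PCP.

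The size is unknown. The assumed cases run from 1.00 to 2.0 when true risks are equal, and the EMR alert pulls the ratio towards 1.00. Serious or medically attended events are less exposed, provided that the alert works as described. The conclusion rests on the documents as supplied and would weaken if the scripts or the Manual of Procedures already contain one identical question for both arms. Nothing here touches the primary or secondary efficacy analyses. It is a cheap improvement worth making.

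**What to change.** 1. In 8.2, remove the home-exercise wording so that the scope matches 8.3.4.
2. At the blinded 6- and 12-month phone assessments, add one short scripted adverse event question set, identical in both arms. Fix the recall period (for example, since the last assessment), do not ask about cause, and place it after the WOMAC and all other outcome measures.
3. State that adverse events will be reported by arm and by capture route. Use the scripted answers for any between-arm summary; keep coach and EMR reports for individual safety reporting.

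The cost is a few minutes on at most 240 × 2 = 480 calls already planned, one data-entry form, a wording change, and more adverse event forms to review. With equal capture of, say, 80% in both arms, the expected recorded ratio is 1.00 when true risks are equal.

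There are two downsides. Recall of minor events over months is imperfect, though no text-based reason suggests it would differ by arm through the question itself. There is also a small risk that an answer reveals the arm to the assessor. Asking last protects that call's measures, and not asking about cause helps. It does not fully protect the 12-month call if the same assistant made the 6-month one, so the assessor should note any apparent unblinding.
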